Type 2 diabetes (T2D) is a global health problem affecting more than 370 million people worldwide. According to the estimations of the International Diabetes Federation, Bosnia and Herzegovina has one of the highest prevalence of diabetes in Europe, 12.3%.¹ Despite development of novel pharmacological agents, sulfonylureas (SUs) remain the most commonly prescribed drugs after metformin in the treatment of T2D, because of their high efficacy, extensive experience and least cost.² Due to their low cost compared to some of the newer agents, SUs are particularly widely used in low and middle income countries, where they have been recommended as treatment of choice for T2D.³ The most common and potentially most serious adverse effect of sulfonylurea therapy is hypoglycaemia.⁴ Severe hypoglycaemia may result in significant morbidity, including higher risk of dementia, stroke and mortality.⁵⁻⁷ Among different SUs, gliclazide has been recommended as a first choice in many countries, as it seems to be associated with lower risk of hypoglycaemia and lower morbidity and mortality compared with other SUs.^{8,9} Furthermore, gliclazide has been included on the WHO Model List of Essential Medicines, based on safety data in elderly patients. Nevertheless, in a recent population-based cohort study, gliclazide showed a similar risk of hypoglycaemia compared with other SUs.¹⁰

Gliclazide is extensively metabolised in the liver to inactive metabolites. Although CYP2C9 is involved in the metabolism of gliclazide,¹¹ the pharmacokinetics (PK) and pharmacodynamics (PD) of gliclazide seem to be affected mainly by *CYP2C19* genetic polymorphisms.^{12,13}

Gastrointestinal problems, such as gastroesophageal reflux disease (GERD) are common in T2D.¹⁴ A recent meta-analysis involving 9,067 cases and 81,968 controls showed a significant association between diabetes and the risk of GERD.¹⁵ The prevalence of GERD symptoms in patients with T2D could be as high as 40%.¹⁴ Therefore, millions of individuals are managing blood glucose and GERD concomitantly.¹⁶ Proton pump inhibitors (PPIs) are the medications of choice for GERD, and are primarily metabolised by CYP2C19.¹⁷ The potential for drug-drug interactions is highest for omeprazole and its stereo-isomer esomeprazole, which are metabolised almost entirely by CYP2C19.^{17,18} Furthermore, it has been shown that impact of PPIs on the PK, PD, and therapeutic response to drugs metabolised by CYP2C19 could depend on *CYP2C19* genotype, with highest effect seen in CYP2C19 normal metabolisers (extensive metabolisers, EM)^{19,20} and ultrarapid metabolisers (UM).²¹

Project aims

Considering the high prevalence of use of PPIs,²² the greater incidence of GERD in T2D and likely high concomitant use of PPIs with gliclazide, and the possibility of their interaction via CYP2C19, the primary aim of this pilot clinical study is to explore potential drug-drug interaction between gliclazide and omeprazole in CYP2C19 EM/UM metabolisers. The specific aims are:

1. To explore whether gliclazide PK is altered upon co-administration with omeprazole in healthy volunteers, CYP2C19 EM/UM metabolisers
2. To explore whether gliclazide PD is altered upon co-administration with omeprazole in healthy volunteers, CYP2C19 EM/UM metabolisers

Preliminary data

To our knowledge, there have been no studies exploring potential interaction between any PPI and gliclazide, in animals or humans. To explore this possible drug-drug interaction, we performed preliminary observational analyses in the large population-based GoDARTS study (UK). Briefly, our preliminary data suggest that co-treatment with PPIs, especially omeprazole, increases the risk of hypoglycaemia in patients with CYP2C19 EM/UM phenotype treated with gliclazide. This has been confirmed by better glycaemic response (lower HbA1c) associated with PPI use in EM/UM patients treated with gliclazide. These results support a biologically plausible hypothesis of possible interaction between PPIs and gliclazide, in relation to CYP2C19 genotype.

Study population

The study protocol will be approved by the Ethics Committee of the General Hospital "Prim. [name]" and the Ethics Committee of the Faculty of Medicine, University of Sarajevo, Sarajevo, Bosnia and Herzegovina (B&H). All procedures will be conducted at the Department of Internal Medicine of the General Hospital in line with the Good Clinical Practice and the Declaration of Helsinki. Prior to inclusion in the study, the nature and purpose of the study will be explained, in both written and verbal form, to each volunteer who will then give the informed written consent to participate in the study.

Volunteers will be initially recruited through advertising by using leaflets, posters and social networks (e.g. Facebook). At least 40 volunteers will be recruited and pre-screened for CYP2C19 genotype. Based on the frequency of CYP2C19*2 variant in B&H population of ~17%,²³ we expect that about two-thirds of screened individuals will be non-carriers of the *2 allele. The recruitment will end when the minimal number of 16 individuals, non-carriers of *2 allele, is reached. Only these individuals (CYP2C19 EM/UM metabolisers) will be included in the drug interaction study after confirmation of their health status.

Inclusion criteria for screening (genotyping)

- Men
- Age 18-30 years
- Non-smokers

Exclusion criteria for screening (genotyping)

- medical history of hepatic, renal, gastrointestinal and hematologic disease or any acute or chronic disease
- any chronic drug therapy
- drug allergy to sulfonylureas and/ or PPIs
- history of drug abuse

Genotyping

Genomic DNA will be extracted from blood samples by using commercial DNA extraction kits. Polymorphisms in the CYP2C19 gene: CYP2C19*2 (rs4244285) and CYP2C19*17 (rs12248560), CYP2C9 gene: CYP2C9*2 (rs1799853), CYP2C9*3 (rs1057910) and a variant in the POR gene encoding a CYP450 redox partner, enzyme P450 oxidoreductase (POR), POR*28 (rs1057868), will be genotyped by specific Drug Metabolism SNP genotyping assays. Genetic test results for CYP2C19 variants will be obtained at the screening, before the randomisation. Only individuals, non-carriers of the CYP2C19*2 allele will be included further in the clinical study. Results obtained for other three variants in the CYP2C9 and POR genes will be used as covariates in the statistical analysis.²⁴

[figure not shown]
Inclusion criteria for drug interaction study

- CYP2C19 normal/ ultrarapid metabolisers (non-carriers of the *CYP2C19**2 allele)

Exclusion criteria for drug interaction study

- abnormalities in physical examination, ECG and routine clinical laboratory tests (including fasting blood glucose concentration)
- medication use during the 14 days prior and during the study periods
- grapefruit, grapefruit juice, alcohol, beverages or food containing methylxanthines use during 72 h prior and during the study periods

Participants will be randomised to specific treatment sequences using SAS Proc Plan procedure.

Drug interaction study design

A randomised, placebo controlled, two-sequence, two-period crossover study, with at least a 7-day washout period between the study periods will be conducted to compare the effects of gliclazide (40 mg, half of an 80 mg tablet of Diprian[®], Hemofarm d.o.o. Banja Luka, B&H, orally) and placebo with those of gliclazide combined with omeprazole (20 mg, Ulcosan[®], Bosnalijek d.d. Sarajevo, B&H, orally). Prior to administration of gliclazide, omeprazole or placebo will be administered once daily at 8 AM for 4 days (on day 1 until day 4) to assure PD steady-state. At 8 AM of the day 5, after an overnight fast (last meal at 9 pm of the previous day), the participants will be given a single dose of 40 mg gliclazide with 240 mL of water together with omeprazole or with placebo according to their treatment assignment.

The volunteers will be given both drugs (gliclazide + omeprazole or gliclazide + placebo) in a sitting position and they will not be permitted to lie down or sleep for the next 4 h after taking gliclazide. They will be under direct medical supervision throughout the 24 h following drug administration.

In order to counteract the blood glucose-lowering action of gliclazide, subjects will receive standardized meals: a breakfast at 30 min after gliclazide intake, snacks after 2 and 3 h, a lunch (warm meal) after 4 h, a snack after 6 h, a dinner after 8 h, and additional snacks at 10 h and 12 h after drug administration. The larger meals should be eaten within 10 minutes, and snacks within 5 minutes. No other food and drink (with the exception of water) or strenuous activities will be allowed.

[figure not shown]
Schematic design of the drug interaction study

- Period 1
 - Eight (8) subjects will receive treatment A on days D 1–5
 - Eight (8) subjects will receive treatment B on days D 1–5
- Wash-out period D6–14
- Period 2
 - Eight (8) subjects will receive treatment B on days D 15–19
 - Eight (8) subjects will receive treatment A on days D 15–19

Treatment

Treatment A: days 1–4, administration of placebo with 240 mL of water
day 5, administration of placebo + 40 mg gliclazide with 240 mL of water

Treatment B: days 1–4, administration of 20 mg omeprazole with 240 mL of water
day 5, administration of 20 mg omeprazole + 40 mg gliclazide with 240 mL of water

*Wash-out period of at least 7 days

Blood collection

Venous blood samples will be collected on day 5 and day 19 for gliclazide, glucose and insulin quantification, through an indwelling intravenous cannula in the arm or by direct venepuncture (in the case of cannula blockage).

A total of 17 blood samples, 5 ml each, will be taken, thus the total blood volume of 85 ml will be taken during 24 hours, which is over 5 times less than the standard 450 ml drawn during voluntary blood donation.

Blood sampling for gliclazide quantification

- gliclazide: pre-dose (0 h), 0.5, 1, 1.5, 2, 2.5, 3, 3.5, 4, 4.5, 5, 6, 7, 8, 10, 12, and 24 h

Blood sampling for glucose and insulin quantification

- glucose: pre-dose (0 h), 0.5, 1, 1.5, 2, 2.5, 3, 3.5, 4, 4.5, 5, 6, 7, 8, 10 and 12 h
- insulin: pre-dose (0 h), 0.5, 1, 1.5, 2, 2.5, 3, 3.5, 4, 4.5, 5, 6, 7, 8, 10 and 12 h

Blood glucose levels will be measured immediately after sampling. Serum samples for insulin and gliclazide quantification will be obtained and stored in properly labelled tubes at -80°C until the analysis.

Gliclazide concentration analysis

Serum gliclazide concentration will be analysed at the Biomarker and Drug Analysis Core Facility, School of Medicine, University of Dundee, by using a stable isotope dilution LC-MS method.

Glucose and insulin quantification

Glucose concentrations will be measured at the laboratory of the General Hospital.

Insulin concentrations will be quantified by enzyme-linked immunosorbent assay (ELISA) using commercially available kit.

Pharmacokinetic analysis

- C_{max} : Gliclazide maximum concentration
- t_{max} : Time to reach C_{max}
- AUC_{0-t} : Area under the concentration–time curve (AUC) up to the last concentration measured
- $\text{AUC}_{0-\infty}$: Area under the concentration–time curve (AUC) extrapolated to infinity
- $t_{1/2}$: Elimination half-life
- $C_{\text{L}/\text{F}}$: Apparent oral clearance
- $V_{\text{d}/\text{F}}$: Apparent volume of distribution

PK parameters will be calculated by a noncompartmental analysis using PKSolver a program for PK and PD data analysis in Microsoft Excel. Gliclazide maximum concentration (C_{max}) and time to reach C_{max} (t_{max}) will be determined by the inspection of the concentration–time data. The area under the plasma gliclazide concentration–time curve (AUC) up to the last concentration measured (AUC_{0-t}) will be determined using the linear trapezoidal rule. The AUC will be extrapolated to infinity ($\text{AUC}_{t-\infty}$) using C_t/k_{el} , where C_t is the last measured gliclazide concentration and k_{el} is the elimination rate constant that will be estimated from the slope of the best-fit line determined by linear regression analysis of the log-transformed concentration-time curve. The elimination half-life ($t_{1/2}$) will be calculated using the following equation: $t_{1/2}=\ln(2)/k_{\text{el}}$. The apparent oral clearance (CL/F) will be calculated as $\text{dose}/\text{AUC}_{0-\infty}$. The apparent volume of distribution ($V_{\text{d}/\text{F}}$) will be calculated as $\text{dose}/\text{AUC} \times k_{\text{el}}$.

Pharmacodynamic parameters

- C_{\min} : Glucose minimum concentration
- $C_{\text{avg } 0-4}$: Average glucose concentration in the period 0–4 h
- $C_{\text{avg } 0-12}$: Average glucose concentration in the period 0–12 h
- AUC_{0-4} : Area under the glucose concentration–time curve from 0 to 4 h
- AUC_{0-12} : Area under the glucose concentration–time curve from 0 to 12 h

- C_{\min} : Insulin minimum concentration
- $C_{\text{avg } 0-4}$: Average insulin concentration in the period 0–4 h
- $C_{\text{avg } 0-12}$: Average insulin concentration in the period 0–12 h
- AUC_{0-4} : Area under the insulin concentration–time curve from 0 to 4 h
- AUC_{0-12} : Area under the insulin concentration–time curve from 0 to 12 h

To compare the PD effects of gliclazide, the areas under the glucose and insulin concentration–time curve from 0 to 4, and 0 to 12 h after the administration of gliclazide will be calculated using the linear trapezoidal rule. The minimum glucose and insulin concentration will be determined by observation of the concentration–time data, and mean concentrations from 0 to 4 h and from 0 to 12 h will be calculated by dividing the area under the glucose/insulin concentration–time curve by the corresponding time interval.

Safety assessment and precaution measures

The volunteers will undergo a detailed physical, ECG, and laboratory examination upon inclusion in the drug interaction study. The subjects will be contacted within 14 days of study completion in order to confirm the adequate post-study status.

If any clinical reasons arise that could endanger health status of the subjects by taking blood samples, the blood samples will not be drawn. Considering that bruising, bleeding, infection or pain may occur at the site of venepuncture and cannulation, these procedures will be performed by experienced medical staff to minimise the risk of excessive bleeding or bruising, and a topical anaesthetic may be used, if required, to reduce the pain.

Since this combination of drugs can potentially induce risk of hypoglycaemia, administration of the two drugs will be carried out in the hospital where the subjects will be hospitalised for 24 h and will be continuously under direct medical supervision. In order to avoid the risk of hypoglycaemia, subjects will receive 8 meals (breakfast, lunch, dinner and 5 snacks). In case of any symptom suggestive of hypoglycaemia (nervousness, sweating, intense hunger, trembling, weakness, palpitations), the blood glucose level will be measured using a glucometer and one of the standard measures of raising blood sugar will be applied, such as administration of 20% oral glucose solution, glucose solution for intravenous use, or glucagon for intramuscular use.

In addition, systolic and diastolic blood pressure and heart rate will be measured in the supine position after a 5-minute rest, before drug intake and during the PK profiles at 2, 4, 12 and 24 hours after gliclazide administration.

Power analysis

For identification of clinically relevant drug-drug interaction, we will use the bioequivalence approach. The main outcome to be evaluated is the exposure to gliclazide, expressed as AUC_{0-t} . Sample size calculation was performed using SAS Proc Power procedure for equivalence test in 2x2 crossover design.²⁵ For an equivalence range of 80–125%, the within-subject coefficient of variation for the AUC values for gliclazide of 7.8% based on previous PK studies,^{26,27} and expected test/reference geometric

mean ratios between 87–115%, 14 volunteers (7 individuals per sequence) are required to show the lack of interaction with 85% power. To account for potential drop-outs due to non-compliance or loss of follow up (assuming a drop-rate of 10%), a total of 16 subjects, CYP2C19 EM/UM metabolisers, will be randomised. To achieve this number, minimally 40 volunteers will be initially recruited.

Statistical analysis

The geometric mean will be calculated for each PK and PD parameter. Logarithmic transformation will be used for PK variables, except t_{max} , before the analysis. The ratios of the geometric means with 90% confidence intervals (CI) will be assessed by linear mixed models between the two treatment assignments: gliclazide and omeprazole coadministration to that of gliclazide and placebo. The statistical analyses will be performed using the SAS 9.3 software (SAS Institute Inc., Cary, NC).

Original scientific contribution and clinical significance of the research

This research will establish whether omeprazole can alter PK/PD of gliclazide, and thus increase the risk of serious hypoglycaemia with this recommended SU drug.

This study can unravel new, previously unrecognized drug-drug and drug-drug-gene interactions. If clinically relevant alterations in gliclazide PK/PD parameters are established, our findings can lead to changes in clinical practice with the aim of preventing serious, potentially life-threatening hypoglycaemia induced by gliclazide treatment.

Confidentiality and data protection

All clinical, laboratory and genetic data will be processed in a manner designed to protect the identity of the participants, in accordance with the rules of personal data protection and the guidelines of the Good Clinical Practice. Participants' privacy will be respected in all published and other public written data that will result from this study.

Withdrawal from the study

Participants are free to withdraw from the study at any time, without obligation to explain their decision.

Insurance

In accordance with the guidelines of Good Clinical Practice, the subjects will be insured under the terms of insurance for Clinical Trials.

Compensation of costs

The costs of participants arising from their participation in the screening visit will be reimbursed in the amount of 50.00 BAM upon completion, and the costs of participants arising from their participation in the drug interaction study will be reimbursed in the amount of 400.00 BAM upon completion of the study. The funds will be paid to the participants' bank account.

Adverse events

Definitions

An *adverse event* (AE) is any untoward medical event affecting a clinical trial participant. Each initial AE will be considered for severity, causality or expectedness and may be reclassified as a serious event or reaction based on prevailing circumstances.

An *adverse reaction* (AR) is where it is suspected that an AE has been caused by a reaction to a trial drug.

A serious adverse event (SAE), serious adverse reaction (SAR) or suspected unexpected serious adverse reaction (SUSAR) is any AE, AR or UAR that at any dose:

- results in death or is life threatening
- requires hospitalisation or prolongation of existing hospitalisation
- results in persistent or significant disability or incapacity
- is a congenital anomaly or birth defect.

Recording and reporting adverse events and serious adverse events

The principal investigator should report any SAE that is both related to the research procedures and is unexpected, to the Ethics Committees which approved the study, and to the Faculty of Pharmacy University of Sarajevo, within 24 hours of the becoming aware of the event.

An adverse event log will be maintained in the CRF. The principal investigator on this study is medically qualified and will assess all adverse events for expectedness, seriousness and causality and will follow up to resolution or to within 30 days of the end of the study. The seriousness of the adverse event will be graded according to the *Common Terminology Criteria for Adverse Events (CTCAE) v5.0 Publish Date: November 27, 2017* (https://ctep.cancer.gov/protocoldevelopment/electronic_applications/docs/CTCAE_v5_Quick_Reference_5x7.pdf).

References

1. Feng, Y., *et al.* Ser1369Ala variant in sulfonylurea receptor gene ABCC8 is associated with antidiabetic efficacy of gliclazide in Chinese type 2 diabetic patients. *Diabetes Care* **31**, 1939-1944 (2008).
2. Standards of Medical Care in Diabetes-2017: Summary of Revisions. *Diabetes Care* **40**, S4-S5 (2017).

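### Does stopping recruitment at 16 non-carriers, counted before the health check, leave the trial short of its 16 randomised men?

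*Combined protocol and SAP*

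**What the plan says.** The Study population section gives a screening number: "At least 40 volunteers will be recruited and pre-screened for CYP2C19 genotype". It puts the *2 allele frequency at about 17% and expects roughly two-thirds of those screened to be non-carriers. It then gives a stopping sentence: "The recruitment will end when the minimal number of 16 individuals, non-carriers of *2 allele, is reached". Those men "will be included in the drug interaction study after confirmation of their health status".

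The section on exclusion criteria for the drug interaction study lists what can remove a man after genotyping, including "abnormalities in physical examination, ECG and routine clinical laboratory tests (including fasting blood glucose concentration"). No failure rate is given for these checks.

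The Power analysis asks for 14 evaluable men and adds a 10% allowance for non-compliance and loss to follow-up, so that "a total of 16 subjects, CYP2C19 EM/UM metabolisers, will be randomised". It then repeats the screening minimum: "To achieve this number, minimally 40 volunteers will be initially recruited".

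**The concern.** Two features look wrong on first reading.

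- The plan seems to have two end points for recruitment. One is a minimum of 40 screened. The other is a stop at 16 non-carriers, which on the plan's own allele frequency should come well before the 40th volunteer. The text does not say how the two fit together.
- The stop counts a different group from the one the sample size needs. It counts men at genotyping, whereas the Power analysis counts men randomised, who have also passed the health check. The 10% allowance names only losses from non-compliance and follow-up, so it does not cover failed health checks.

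If a site followed the stopping sentence alone, any failed health check would leave fewer than 16 to randomise. The equivalence test on gliclazide AUC(0-t) would then be run with fewer men than planned.

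**Working it through.** **Inputs from the documents.** Equivalence range 80–125%; within-subject CV 7.8%; expected ratio 87–115%; 14 evaluable men for 85% power; 10% drop-out; 16 randomised (all Power analysis). 90% confidence interval, hence two one-sided tests at 5% each (Statistical analysis). *2 allele frequency about 17%, about two-thirds non-carriers, at least 40 screened (Study population).

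**Assumption.** The health-check failure rate f is not in the documents. It is shown at 2, 5, 10 and 20%.

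**1. The plan's own figure.** On the log scale σ = √ln(1 + 0.078²) = 0.0779. With n = 14 in a 2×2 crossover, SE = 0.0779 × √(2/14) = 0.0294 on 12 degrees of freedom. Exact power is 85.1% at ratio 0.87 and 84.7% at 1.15, against 85% stated. Drop-out: 14/0.90 = 15.6, rounded up to 16. The sample size is reproduced.

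**2. Where the stop would fall.** Non-carrier share q = 0.83² = 0.689 (Hardy–Weinberg), or 2/3 as the plan rounds it. The expected number screened to reach 16 is 16/0.689 = 23.2, or 16/(2/3) = 24.0. The chance of reaching 16 before the 40th volunteer is above 99.9%. The stop taken alone would therefore nearly always come before the stated minimum of 40.

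**3. If the minimum of 40 is kept.** Expected non-carriers: 40 × 2/3 = 26.7 to 40 × 0.689 = 27.6. The number passing the health check is binomial(40, q(1 − f)), and the expected surplus is 40q(1 − f) − 16.

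| Assumed f | Chance at least 16 pass (q = 2/3; q = 0.689) | Expected surplus over 16 |
|---|---|---|
| 2% | 99.97%; 99.99% | 10.1 to 11.0 |
| 5% | 99.92%; 99.97% | 9.3 to 10.2 |
| 10% | 99.7%; 99.9% | 8.0 to 8.8 |
| 20% | 96.8%; 98.1% | 5.3 to 6.0 |

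**4. If the stop is taken literally.** The chance that all 16 can be randomised is (1 − f)^16. Completers are binomial(16, 0.9(1 − f)). The exact power for each number of completers, with sequences split as evenly as possible, is averaged over that distribution.

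| Assumed f | Chance all 16 randomised | Average power, ratio 0.87 | Average power, ratio 0.90 |
|---|---|---|---|
| 0 (16 randomised) | 100% | 85.7% | 98.3% |
| 2% | 72% | 84.9% | 98.1% |
| 5% | 44% | 83.7% | 97.7% |
| 10% | 19% | 81.5% | 96.9% |
| 20% | 3% | 76.3% | 94.5% |

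A full set of 16 often fails to materialise on this reading, but the loss of power is small unless failures are common and the true ratio lies at the edge of the planned range.

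**The case for a change.** The strongest case for a change is that the stopping sentence, as written, does count the wrong men, and that nothing in the text ranks it against the minimum of 40. A coordinator who reads only that sentence would stop near volunteer 24 with no reserve. At an assumed 10% failure rate there would then be only a 19% chance of randomising all 16. Even with 40 screened, the text does not say how 16 are picked from roughly 21 to 27 eligible men, or whether the rest are reserves. One or two sentences would settle this at almost no cost, since genotyping 40 is already planned.

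The description of the wording stands: the two sentences are not linked, and the count precedes the health check. The consequence does not follow from it. The early stop requires ignoring a minimum that is stated in two sections, and in the Power analysis that minimum is tied directly to obtaining the 16 randomised. The stopping sentence also calls 16 a minimal number, so both conditions can be met together: screen at least 40, and go on if there are still too few non-carriers.

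The selection point carries little weight. Each man is his own control and treatment sequence is randomised, so the order in which eligible men are taken does not bias the within-subject comparison. A figure in the Study population section was not visible to me and may also show the recruitment flow.

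**Conclusion.** No change is needed. This is loose wording that a recruiting team can resolve from the plan itself. Forty is a stated minimum. Keeping to it gives 26.7 to 27.6 expected non-carriers for 16 places, and at least a 96.8% chance of 16 healthy non-carriers even at 20% failure. The margin for failed health checks is there, though it is not named as one. The stated sample size and power are correct.

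Harm needs two things together: a site that stops early against both statements of the minimum, and a high failure rate. The volunteers are non-smoking men aged 18–30, already screened by history for acute and chronic disease and chronic drug therapy, so a low rate is plausible. At 2 to 5% failure, the literal stop costs 0.8 to 2.0 percentage points of average power at ratio 0.87 and 0.2 to 0.6 points at 0.90.

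The conclusion rests on the minimum of 40 being honoured, on a non-carrier share near two-thirds, and on a health-check failure rate within the range shown. The failure rate is an assumption, not a figure from the documents.

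### Scheduled glucose stops at 12 h and the 24 h blood draw is not tested for it, so a 24 h stay arranged because of possible hypoglycaemia can end without a late fasted value

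*Combined protocol and SAP*

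**What the plan says.** Under Blood sampling for glucose and insulin quantification, the glucose times are "glucose: pre-dose (0 h), 0.5, 1, 1.5, 2, 2.5, 3, 3.5, 4, 4.5, 5, 6, 7, 8, 10 and 12 h". The insulin times are the same. The gliclazide list has the same times plus one more, ending "4.5, 5, 6, 7, 8, 10, 12, and 24 h". Under Blood collection the plan states "A total of 17 blood samples, 5 ml each, will be taken", and for glucose, "Blood glucose levels will be measured immediately after sampling".

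Drug interaction study design sets the feeding. Dosing is at 8 AM, "after an overnight fast (last meal at 9 pm of the previous day". Breakfast follows at 0.5 h, then meals and snacks through the day, ending with "additional snacks at 10 h and 12 h after drug administration". Beyond these, the rule is "No other food and drink (with the exception of water".

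Safety assessment and precaution measures explains that volunteers are kept in hospital for 24 h, watched by medical staff throughout, because the combination might cause hypoglycaemia. Outside the sampling schedule, a glucometer reading is taken if symptoms suggest it, and oral, intravenous or intramuscular rescue is available. Blood pressure and heart rate are scheduled before dosing and at 2, 4, 12 and 24 h. No glucose check before discharge is described.

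**The concern.** The plan names a hazard and sets a 24 h window of observation for it, yet the measurement that shows the hazard directly is scheduled for only half of that window. Scheduled glucose also ends at the point where feeding ends, and the meals are there to offset the drug's glucose-lowering effect. The remaining 12 h have no scheduled food and no scheduled glucose.

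In that half the only trigger for a reading is a symptom. Several of the listed symptoms, such as hunger, nervousness or weakness, depend largely on the volunteer reporting them. Sleep is barred only for the first 4 h after dosing, so these hours include the night, when self-report is weakest.

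At stake is a safety check in healthy volunteers who gain nothing from the drug. The analysis is not at stake.

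**Working it through.** **Inputs.** Sampling times come from the Blood sampling sections, draw count and volume from Blood collection, and meal times and dosing hour from Drug interaction study design. The 16 volunteers and two periods come from the power analysis and the design. The arithmetic assumes that all 16 complete both periods.

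**The plan's own figure first.**
- Gliclazide times: 0, 0.5, 1, 1.5, 2, 2.5, 3, 3.5, 4, 4.5, 5, 6, 7, 8, 10, 12, 24 h = 17.
- Volume: 17 × 5 ml = 85 ml. This agrees with the plan.

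**Coverage of the stay.**
- Glucose times: the same list without 24 h = 16, all within 0–12 h.
- Scheduled glucose values in 12–24 h, after the 12 h sample: 0.
- The only draw not tested for glucose is the one at 24 h.

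**Time since food at each scheduled glucose value.** Food is given at 0.5, 2, 3, 4, 6, 8, 10 and 12 h. A sample due at the same time as food is taken to come before it.

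| Sample (h) | Last food (h) | Hours since food |
|---|---|---|
| 1 | 0.5 | 0.5 |
| 1.5 | 0.5 | 1 |
| 2 | 0.5 | 1.5 |
| 2.5 | 2 | 0.5 |
| 3 | 2 | 1 |
| 3.5 | 3 | 0.5 |
| 4 | 3 | 1 |
| 4.5 | 4 | 0.5 |
| 5 | 4 | 1 |
| 6 | 4 | 2 |
| 7 | 6 | 1 |
| 8 | 6 | 2 |
| 10 | 8 | 2 |
| 12 | 10 | 2 |
| 24 (not tested) | 12 | 24 − 12 = 12 |

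From 1 h on, no scheduled glucose value lies more than 2 h after food. The 0.5 h sample, if taken before breakfast, is still fasted, but it comes only half an hour after the dose. Of the blood already being drawn, only the 24 h sample follows a long post-dose fast.

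**Comparison with baseline.** The pre-dose sample follows a fast from 9 PM to 8 AM, 11 h. The 24 h sample follows one from 8 PM to 8 AM, 12 h. The two fasts are of similar length.

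**Size of the change.**
- Volunteer-periods: 16 × 2 = 32.
- Glucose measurements now: 16 × 32 = 512.
- With 24 h added: 512 + 32 = 544, and 32/512 = 6.25%.
- Draws remain 17 and volume 85 ml per period.

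**What cannot be computed.** The documents give no gliclazide half-life, no concentration–effect relation and no late event rate. The probability of a low value after 12 h cannot be derived from them.

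**The case against.** The strongest reply is that stopping at 12 h is deliberate and coherent. The average and area PD parameters are defined over 0–4 h and 0–12 h, so the glucose schedule matches what it feeds. Safety is handled by other means: eight feeds, continuous supervision, symptom-triggered readings, rescue treatment, vital signs at 12 and 24 h, and contact within 14 days. The volunteers are healthy young men given one 40 mg dose. No harm has been quantified, and a single value at 24 h does not cover the night.

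Most of this is true, and it limits the weight of the point. The 12 h stop is consistent with the PD parameters, absolute risk is low, and an overnight low would still be found only through supervision and symptoms.

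Three further reservations also stand:
- The 12 h fast rests on reading the ban on other food as lasting until the 24 h draw. The text gives no end time.
- The baseline match is imperfect. The 9 PM meal is not standardised, whereas the 24 h sample follows a day of standardised feeding.
- The documents give no numerical threshold for a low value.

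None of this supplies the missing check. An asymptomatic volunteer can still leave with no glucose value after 12 h. Staff may test before discharge in practice, but the plan does not require it.

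**Conclusion.** The concern holds as a modest gap in safety monitoring. Each volunteer-period has 16 scheduled glucose values in 0–12 h and none in the following 12 h, across 32 volunteer-periods. The longest post-meal interval at any scheduled value from 1 h on is 2 h, against 12 h at the untested 24 h draw. The scheduling facts are certain. The size of the late risk is unknown, and no figure is put on it.

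The conclusion rests on two readings: no food is given between the 12 h snack and the 24 h draw, and the sampling list is complete as written. It does not touch the primary outcome (gliclazide AUC0–t), the sample size, or the 0–4 h and 0–12 h PD parameters. The change should be made because it tests blood already in hand for the risk the plan itself names, but the study does not fail without it.

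**What to change.** - **Blood sampling for glucose and insulin quantification:** add 24 h to the glucose list, measured at once in the sample already drawn for gliclazide and before any breakfast. Leave the insulin list unchanged.
- **Safety assessment and precaution measures:** require the supervising physician to see the 24 h result before the volunteer leaves. A low value is treated and the measurement repeated first. What counts as low can be left to that physician or written into the amendment.
- **Pharmacodynamic parameters:** the plan says "The minimum glucose and insulin concentration will be determined by observation" of the data and gives no time window. Define Cmin for glucose and insulin as the minimum over 0–12 h, so that the added value cannot alter a planned parameter.
- **Reporting:** show the 24 h fasted glucose by treatment beside the pre-dose value, as an additional safety and exploratory result.
- **Optional:** bedside glucometer readings between 12 and 24 h, if the investigators want cover for the night itself.

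The cost is a short amendment and 32 more glucose measurements, with no extra draw and no extra insulin assay. Volunteers wait briefly for the 24 h result, and lose some sleep only if the optional overnight readings are used.
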